4.1 INTERIM ANALYSES

The study will incorporate a group sequential design (GSD) in which an interim analysis will be performed to detect an 80% protective effect of the Tango Belt at 80% power. If a significant difference is found between the prospective Tango Belt subjects and historical controls at the interim analysis, the study will be stopped, and the Tango Belt deemed superior to SOC alone. If not, sample size reestimation will be completed, and enrollment will continue until a final sample size is reached to detect a 60% protective effect of the Tango Belt at 80% power and a 5% total level of significance.

Following the steps from section 4, we assumed subjects were followed for an average of 6 months, an annual fall-with-major-hip-injury rate of 15%, and sufficient historical control subjects to allow 1:2 allocation of subjects to treatment and control. This would require 134 subjects in the prospective Tango Belt group and 268 subjects in the historical control group at the interim analysis using the Pocock alpha-spending function as well as accounting for 30% attrition. At the end of the study (should the higher effectiveness target not be achieved at interim analysis), 268 total subjects would be required in the prospective Tango Belt group and 536 subjects would be in the historical control group.

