10.1 Statistical Sample Size Determination and Analytical Plans

Historical control data will be utilized from data available in the medical record. Specifically, the rate of falls with major injury will be obtained and analyzed in 6-month retrospective periods from Investigational sites participating in the prospective enrollment of treatment subjects, beginning with the IRB approval date and extending back to 2018. Due to the COVID-19 pandemic restrictions, it is possible that some subjects at participating Investigational sites did not receive the SOC during this time

period. Therefore, if there is any evidence that the rate of falls resulting in major injuries is different for any portion of the 2018–present time frame, historical control data will not be utilized from the time frames with a different fall rate. The sample size for the control group, and therefore the allocation ratio, will be determined by the number of historical controls for which data is available during the selected time periods. It is anticipated that control data will be available to allow 2, 3, or 4 controls for each treatment subject. The annual rate of falls with major hip injury has been estimated between 6% and 10% in higher-risk populations within long-term care facilities. Since the fall rate is not exactly known in the study population, the fall rate observed in the historical control group, a nuisance parameter, will be used for sample size calculations.

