To estimate performance of the Tango Belt, data on file from real-world use of the Tango Belt in the nursing home setting found airbag deployment in 6 of 6 total serious hip-impacting falls, resulting in no major hip injuries. Therefore, we are 95% confident that the Tango Belt will protect 66% of falls. However, it is possible that the Tango Belt may prove to be even more effective with a larger sample size. Therefore, a group sequential design (GSD) will be utilized. The GSD will include a planned interim analysis at a sample size to detect an 80% protective effect of the Tango belt at 80% power at a planned interim analysis. If a significant difference is found between the prospective Tango Belt subjects and historical controls at the interim analysis, the study will be completed early. If not, enrollment will continue until a final sample size is reached to detect a 60% protective effect of the Tango belt at 80% power and a 5% total level of significance. Exact sample sizes for the interim and final analysis will be calculated once the number of historical control subjects and the rate of falls with major hip injury in the control group are determined. The PASS GSD module will be used to simulate the sample sizes and power using the Pocock alpha-spending function. The steps to calculate the sample size will include:

- 1. Test the historical control time periods to determine if all the time periods can be used, depending on if any time periods differ in fall rate
- 2. From the remaining historical control data, find the fall rate and the total sample size available for the historical control group
- 3. Find the sample sizes for the historical controls and the prospective Tango Belt arm at the interim analysis.
- 4. Find the sample size for the prospective Tango Belt arm at the final analysis; the total sample of historical controls will be used at this look.

To demonstrate these calculations, we assumed subjects were followed for an average of 6 months, an annual fall-with-major-hip-injury rate of 8%, and sufficient historical control subjects to allow 1:4 allocation of subjects to treatment and control. This would require 176 subjects in the prospective Tango belt group and 704 subjects in the historical control group at the interim analysis. At the end of the study (should the

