ENDPOINTS	The study will Investigate the safety and effectiveness of the Tango Belt with the primary and secondary endpoints being taken every 3 months and at the end of the study run time from the electronic medical record. Additionally, ancillary endpoints on adverse events and device performance will be gathered. Primary:

The study's **primary effectiveness endpoint** is the proportion of major hip injuries due to fall in the subjects receiving SOC as compared to subjects receiving SOC plus the Tango Belt.

There is no primary safety endpoint for this study. This is a non-significant risk study. Safety of the device will be determined by analysis of adverse events as an ancillary endpoint.

Secondary:

The study's **secondary endpoints** include the proportion of each of the following:

- Hip fractures due to fall in the subjects receiving SOC as compared to subjects receiving SOC plus the Tango Belt.
- Emergency Department (ED) visits due to fall in the subjects receiving SOC as compared to subjects receiving SOC plus the Tango Belt.
- Hospitalizations due to fall in the subjects receiving SOC as compared to subjects receiving SOC plus the Tango Belt.

Ancillary:

Ancillary endpoints will include:

- Adverse events
- Major injuries due to fall
- Fall occurrence
- Device wear adherence
- Device fall alerts
- Device discrimination of serious hip-impacting vs. non-serious hip and non-hip impacting falls
- Airbag deployment
- Falls Efficacy Scale International (FES-I) short version

INTERIM ANALYSES

The study will incorporate a group sequential design (GSD) in which an interim analysis will be performed to detect an 80% protective effect of the Tango Belt at 80% power at a planned interim analysis. If a significant difference is found between the prospective Tango Belt subjects and historical controls at the interim analysis, the study will be completed early.

If not, enrollment will continue until a final sample size is reached to detect a 60% protective effect of the Tango belt at 80% power and a 5% total level of significance.

It was assumed subjects were followed for an average of 6 months, an annual fall-with-major-hip-injury rate of 15%, and sufficient historical control subjects

	to allow 1.2 allocation of subjects to treatment and central. This would require
	to allow 1:2 allocation of subjects to treatment and control. This would require
	94 subjects in the prospective Tango Belt group and 188 subjects in the

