4 SAMPLE SIZE

It is estimated that the sample size will include up to 268 subjects in the intervention group and up to 536 subjects in the historical control group. This estimated sample size includes the minimum sample size required to assess the primary endpoint with an additional 30% increase to account for possible subject attrition.

The sample size for the primary hypothesis will be calculated with 80% power. The annual rate of falls with major hip injury has been estimated between 6% and 10% in higher-risk populations within long-term care facilities. Since the fall rate is not exactly known in the study population, the fall rate observed in the historical control group, a nuisance parameter, will be used for sample size calculations. After roughly 70% of subjects were enrolled into the historical control group, the proportion of subjects who experienced a major hip injury due to a fall was calculated to be 15% and this rate was used in the sample size calculation.

The following steps were used to calculate the sample size (for further details, see section 10.1 of the Protocol):

1. Test the historical control time periods to determine if all the time periods can be used, depending on if any time periods differ in fall rate

- 2. From the remaining historical control data, the fall rate was calculated and the total sample size available for the historical control group
- 3. The sample sizes for the historical controls and the prospective Tango Belt arm at the interim analysis was calculated.
- 4. The sample size for the prospective Tango Belt arm at the final analysis was calculated using the total sample of historical controls.

This sample size determination was made based on the following specifications:

Primary Effectiveness Endpoint Assumptions:

The following assumptions were made for estimating sample size for the primary effectiveness endpoint:

- 1. Alpha of 0.025 (one-sided)
- 2. 80% power
- 3. Groups are independent

Based on the above assumptions, the minimum sample required for the intervention group for evaluation of effectiveness (unadjusted) is 94 subjects. At least 134 subjects will be enrolled to the intervention group to account for subject attrition and missing data (estimated to be 30%).

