4.1.1 Sample Size Re-Estimation

At the time of interim analysis, if the study is not stopped early for effectiveness, then sample size reestimation (SSRE) will be performed to calculate the final analysis sample size. The SSRE will be calculated the same way as was performed prior to the trial with the addition of a propensity score matching rate. This rate will account for the percentage of subjects that were in the Tango Belt treatment group but were not able to match adequately with any subjects in the historical control

group. The annual fall-with-major-hip-injury rate will be updated using data from the 134 subjects in the Tango Belt treatment group as well.

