9 SUMMARY OF CHANGES FROM THE PROTOCOL

The following table provides a list of changes from the protocol to the SAP, and the justification for each change.

Section	Description	Justification
4. Sample Size	Estimated attrition was changed from	After roughly half the subjects in the
	20% to 30%	Tango Belt group were exited, the
		attrition rate was reexamined and
		adjusted upwards to account for the
		higher-than-expected loss.
4. Sample Size	Historical Control rate of major hip	The sample size estimate was revisited
	injury estimate changed from 8% to	after it was clear that the expected 1:4
	15%	allocation ratio was not attainable. The
		HC rate of major hip injury was also
		examined and deemed to be much higher
		than estimated at the beginning of the
		trial.

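### The 15% control rate that sizes the trial is an undated proportion in SAP 4 but an annual rate in SAP 2 and 4.1; the stated 80% power holds only if it is a 6-month risk

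*Combined protocol and SAP*

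**What the plan says.** - **SAP 4 (Sample Size).** After roughly 70% of the historical controls were in, "the proportion of subjects who experienced a major hip injury due to a fall was calculated to be 15" percent, and that rate went into the calculation. No observation period is given. The result is that "the minimum sample required for the intervention group for evaluation of effectiveness (unadjusted) is 94 subjects".
- **SAP 4.1 (Interim Analyses).** "we assumed subjects were followed for an average of 6 months, an annual fall-with-major-hip-injury rate of 15" percent.
- **SAP 2 (Summary, Interim Analyses).** "It was assumed subjects were followed for an average of 6 months, an annual fall-with-major-hip-injury rate of 15" percent, as in SAP 4.1. SAP 2 gives 94 belt and 188 control subjects at the interim and 188 and 376 at the end, before 30% attrition.
- **SAP 9 (Summary of Changes).** The control "injury estimate changed from 8% to" 15%. The 8% it replaces is defined in protocol 10.1 as "an annual fall-with-major-hip-injury rate of 8" percent, so SAP 9 also implies that 15% is annual.
- **SAP 3.2.1.** The primary endpoint runs from enrollment to the 180-day visit.
- **Protocol 10.1.** Historical data on falls with major injury "will be obtained and analyzed in 6-month retrospective periods". That sentence concerns major injury in general, not hip injury, but it makes a 6-month window for the 15% plausible.
- **SAP 4.1.1.** At re-estimation, "The annual fall-with-major-hip-injury rate will be updated using data from the 134 subjects in the Tango Belt treatment group as well".

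**The concern.** One number has two meanings that differ two-fold. If 15% is the share of controls injured over a 6-month window, it is the control proportion the test needs. If it is annual and subjects are followed for 6 months, the proportion is about 15% × 0.5 = 7.5%, or 7.8% by constant-hazard conversion (1 − 0.85^0.5).

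Power for a fixed relative reduction depends heavily on the control risk, so the 80% claim cannot be true on both readings. The ambiguity also carries forward. SAP 4.1.1 repeats the calculation in the same way and again calls the rate annual, so an analyst following the printed words could halve it and roughly double the final sample size. That section also adds belt-arm outcomes to a quantity SAP 4 takes from the historical controls. If the belt works, the sizing rate is pulled down.

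**Working it through.** **Inputs.** One-sided alpha 0.025 and 80% power (SAP 4). Effects of 80% at the interim and 60% at the end, 1:2 allocation and Pocock spending (SAP 4.1). Evaluable numbers 94/188 and 188/376 (SAP 2). The interim falls at half the information (94 of 188).

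**Boundaries.** The Lan-DeMets Pocock-type function spends 0.025 × ln(1 + (e − 1) × 0.5) = 0.0155 at the interim. The z limits are 2.157 and 2.201 (nominal one-sided 0.0155 and 0.0139).

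**Formula.** Belt-arm n with k = 2 controls per belt subject, d = p_C − p_T and p̄ = (p_T + 2p_C)/3:

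n₀ = [z_α √(1.5 p̄(1 − p̄)) + 0.8416 √(p_T(1 − p_T) + p_C(1 − p_C)/2)]² / d²

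Continuity-corrected n = (n₀/4) × [1 + √(1 + 6/(2 n₀ d))]²

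**Reproducing the SAP figure.** With 15% used directly at the interim, p_T = 0.03, d = 0.12 and p̄ = 0.11. Then n₀ = (2.157 × √0.14685 + 0.8416 × √0.09285)² / 0.0144 = 81.5, and the corrected n is 93.5, against the stated 94. At the end (15% vs 6%, z = 2.201) the corrected n is 184.6, against 188.

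**Belt-arm n under each reading**

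| Control risk used | Formula | Interim | Final |
|---|---|---|---|
| 15% | pooled, corrected | 93.5 | 184.6 |
| 7.5% | pooled, corrected | 197.3 | 391.7 |
| 7.8% (constant hazard) | pooled, corrected | 189.2 | 375.6 |
| 7.5% | unpooled, uncorrected | 123.5 | 291.6 |
| SAP states | | 94 | 188 |

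**Power at the stated evaluable numbers.** Interim power is by exact enumeration; overall power is from 400,000 simulated two-stage trials.

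| Test | 7.5%: interim, 80% effect | 7.5%: overall, 60% effect | 15%: interim, 80% effect | 15%: overall, 60% effect |
|---|---|---|---|---|
| Pooled z | 47.4% | 49.9% | 88.6% | 87.2% |
| Continuity-corrected | 32.9% | 39.2% | 83.2% | 83.2% |
| Likelihood ratio | 59.9% | 58.4% | 92.6% | 89.2% |
| Unpooled z | 71.0% | 64.3% | 94.3% | 91.2% |

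As an upper check at 7.5%, a single look at one-sided 0.025 with unpooled z gives 76.2% at 94/188 (80% effect) and 68.1% at 188/376 (60% effect).

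**Comparison with the protocol example.** Simulating unpooled z with 8% halved to 4% at the protocol's 176/704 and 417/1688 gives 80.0% interim and 81.5% overall power. The protocol therefore appears to have converted annual to 6-month risk, whereas the SAP numbers fit 15% left unhalved.

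**Re-estimation.** SAP 4.1.1 gives no formula. Assuming simple 1:2 pooling and a true 60% effect, the updated rate is (268 × 0.15 + 134 × 0.06)/402 = 0.12. Sizing on 12% vs 4.8% needs 236.4 belt subjects instead of 184.6 with continuity correction, or 216.0 instead of 168.3 without. Either way the increase is about 28%.

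**The case against.** - **The match to 94 does not identify the sponsor's method.** Protocol 10.1 says sizes are simulated in PASS, and the SAP names no sizing test. The corrected formula that gives 94 fails on the protocol's own example: at 4% with 1:4 allocation it gives 329 and 650, against the stated 176 and 417. The unpooled formula with 15% used directly gives 58 and 137, not 94 and 188. This stands, so the match is suggestive only. It does not rescue the annual reading, which misses 80% under every test tried.
- **A 6-month window is not stated anywhere.** True. The SAP 4 reading supports the power claim only if the window is about 6 months. The endpoint definition makes that plausible but does not establish it.
- **The final number is provisional.** If the trial continues past the interim, SAP 4.1.1 recalculates it. The overall power figures therefore describe the plan as printed, not necessarily the trial as run.
- **More than 94 may be analyzed.** With all 134/268 enrolled subjects contributing full information, unpooled z at 7.5% gives 84% at the interim. That is an upper bound: the 134 exists to absorb 30% loss, imputation does not restore full information, and 268/536 still gives at most 78% at the end.
- **It may be a single wrong word.** It may. But a reader cannot tell from the documents whether the label or the power claim is the error.

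**Conclusion.** The point holds. SAP 4 conflicts with SAP 2 and 4.1, SAP 9 implies the annual reading, and nothing reconciles them. If 15% is a 6-month risk, the stated numbers are adequate (83% to 94% interim, 83% to 91% overall) and the label is wrong. If it is annual, the 80% claim fails: 33% to 71% at the interim and 39% to 64% overall, depending on the test.

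These figures assume 1:2 allocation, Pocock-type spending at half information, the stated evaluable numbers and unadjusted tests of two proportions. The 28% inflation at re-estimation also assumes simple pooling. Its direction, more subjects than needed if the belt works, is an inefficiency rather than a loss of power. This should be fixed before re-estimation, which reuses the rate.

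**What to change.** 1. Confirm from the control data already held what period the 15% covers.
2. If it covers 6 months, remove the word annual and state the window in SAP 2, 4, 4.1 and 4.1.1, and note in SAP 9 that the 15% and the annual 8% it replaces are on different time scales. Suggested wording: *The proportion of historical controls with a major hip injury over the 6-month review window was 15% and was used directly as the control proportion.*
3. If it is annual, recompute with the sponsor's own sizing test, name that test, and restate the power at the stated numbers.
4. In SAP 4.1.1, take the control rate for re-estimation from the historical controls only.

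The cost is a few SAP wording changes and one recalculation from existing data. If 15% proves annual, the sponsor must also state a lower power at the planned size. No added subjects are asked for.

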	historical control group at the interim analysis. Assuming a 30% attrition rate
	due to the fragile nature of this population, the samples sizes would increase
	to 134 and 268 in the prospective Tango Belt group and the historical control
	group, respectively. At the end of the study (should the higher effectiveness
	target not be achieved at interim analysis), 188 total subjects would be
	required in the prospective Tango Belt group and 376 subjects would be in the
	historical control group. Accounting for attrition, 268 and 536 in the
	prospective Tango Belt group and the historical control group, respectively.
FINAL ANALYSES	All final planned analyses identified in this SAP will be completed after the last
	subject has completed the End of Study visit and data entry has been finalized
	for all subjects used for analysis (including historical control subjects).

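### The 80% power attached to 188/376 is not met on the annual 15% rate printed beside it (about 39% to 64%); on 15% as a 180-day proportion it is about 86%

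*Combined protocol and SAP*

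**What the plan says.** - **Design targets.** SAP 4: "The sample size for the primary hypothesis will be calculated with 80% power". SAP 2 and 4.1 set the interim for an 80% protective effect at 80% power, and the final size for a 60% effect at 80% power and a 5% total level. SAP 4 fixes one-sided alpha at 0.025, and SAP 4.1 names Pocock alpha spending.
- **Sizes.** Evaluable: 94 belt and 188 control at the interim, 188 and 376 at the end. SAP 2 introduces the final pair with "target not be achieved at interim analysis), 188 total subjects would be". With 30% attrition, SAP 4.1 prints 134/268 and then "268 total subjects would be required in the prospective Tango Belt group and 536 subjects would be in the historical control group".
- **Rate basis in SAP 4.1 (also SAP 2).** "we assumed subjects were followed for an average of 6 months", with "an annual fall-with-major-hip-injury rate of 15%, and sufficient historical control subjects to allow 1:2 allocation".
- **Rate basis in SAP 4.** After about 70% of controls had been enrolled, "the proportion of subjects who experienced a major hip injury due to a fall was calculated to be 15% and this rate was used". No time window is given, but control records are followed over a 6-month window.
- **Test.** SAP 7.2 tests the primary hypothesis by logistic regression controlling for propensity score. Neither document names the test statistic behind the sizes or mentions a continuity correction.
- **Re-estimation.** SAP 4.1.1: "The SSRE will be calculated the same way as was performed prior to the trial", with a matching rate added and the event rate updated.

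**The concern.** The 15% figure has two time bases in one plan. As an annual rate with 6 months' follow-up, it means about 7.5% of controls have an event in the window. As an observed proportion of controls followed for 6 months, it means 15%. The expected number of control events differs by a factor of two, so both bases cannot give the same power.

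Two things depend on the answer. The first is the trial's stated power, since 188/376 sets the stated maximum enrolment of 268/536. The second is the final size after an unsuccessful interim: SAP 4.1.1 repeats the earlier calculation, but its rate basis is stated in two ways and its test is not stated. Without a continuity correction, 80% two-look power needs about 131 (unpooled) to 163 (pooled) evaluable belt subjects at 15% against 6%, and about 278 to 347 at 7.5% against 3%.

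**Working it through.** **Inputs.** One-sided alpha 0.025, 80% power, Pocock spending, 1:2 allocation, 94/188 then 188/376 evaluable (SAP 2, 4, 4.1). The effect is 80% at the interim and 60% at the end.

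**Boundaries.** The information fraction is 94/188 = 0.5. Spending at look 1 is 0.025 × ln(1 + (e − 1) × 0.5) = 0.0155, so c1 = 2.157. With correlation √0.5 between looks, c2 = 2.201 (nominal 0.0139).

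**Step 1. Reproduce the printed sizes on 15% as a proportion.** With d = pC − pT and p̄ = (pT + 2pC)/3:

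- Pooled: n′ = [c√(1.5 p̄(1 − p̄)) + 0.8416√(pT(1 − pT) + pC(1 − pC)/2)]² / d²
- Continuity-corrected: n = (n′/4)[1 + √(1 + 3/(n′d))]²

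| Look | Pooled | Corrected | Unpooled | Printed |
|---|---|---|---|---|
| Interim, 15% v 3% | 82 | 93.5, so 94 | 58 | 94 |
| Final, 15% v 6% | 169 | 184.6, so 185 | 138 | 188 |

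The corrected formula matches the interim exactly and the final size within 2% (185 against 188). Attrition also agrees: 94/0.7 = 134.3 and 188/0.7 = 268.6.

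**Step 2. Same formulas on the annual wording.** 15% × 6/12 = 7.5%, so 7.5% v 1.5% at the interim and 7.5% v 3% at the end. The interim needs about 174 (pooled), 198 (corrected) or 124 (unpooled). The final look needs about 360, 392 or 292. None is near 94 or 188.

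**Step 3. Power of the printed design for a 60% effect.** At each look, power = Φ((d − c·s0 − k)/s1), where

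- s0 = √(p̄(1 − p̄)(1/nT + 1/nC))
- s1 = √(pT(1 − pT)/nT + pC(1 − pC)/nC)
- k = ½(1/nT + 1/nC) if corrected, otherwise 0; the unpooled test puts s1 in place of s0.

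The looks are combined by a bivariate normal. Pooled example:

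- 15% v 6%: look 1, (0.09 − 2.157 × 0.04105)/0.03575 = 0.04, so 51.6%. Look 2, (0.09 − 2.201 × 0.02903)/0.02528 = 1.03, so 84.9%. Two-look: 86.2%.
- 7.5% v 3%: look 1, (0.045 − 2.157 × 0.03000)/0.02605 = −0.76, so 22.5%. Look 2, (0.045 − 2.201 × 0.02121)/0.01842 = −0.09, so 46.3%. Two-look: 49.4%.

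Two-look power, 94/188 then 188/376:

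| Test | 15% v 6% | 7.5% v 3% |
|---|---|---|
| Continuity-corrected pooled Z | 82.1% (simulated 83.2%) | 40.0% (simulated 39.2%) |
| Unadjusted logistic Wald, simulated | 86.0% | 43.0% |
| Pooled Z | 86.2% (simulated 87.2%) | 49.4% |
| Likelihood ratio, simulated | 89.2% | 58.4% |
| Unpooled Z | 92.3% (simulated 91.2%) | 62.9% (simulated 64.3%) |

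The Wald simulation counts a look with no belt events as not significant.

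**Step 4. Interim label.** At 15% v 3%, 94/188 has 80.4% power (Wald, simulated) or 80.3% (corrected). At 7.5% v 1.5% it has 33% (corrected) to 68% (unpooled) by normal approximation.

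**Step 5. Robustness of the annual reading.**
- A constant hazard gives 1 − √0.85 = 7.8% rather than 7.5%. The table range becomes about 42% (corrected) to 65% (unpooled).
- Using the full 0.025 at both looks gives 57% (Wald) to 72% (unpooled).
- With no attrition at all (134/268 then 268/536), power is 67% (pooled) to 79% (unpooled).

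None of these reaches 80%.

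**The case against.** The strongest defence is that the sizes are sound and only the word annual is misplaced. SAP 4 says a proportion was used. On that basis a standard continuity-corrected formula gives 94 and 185, with about 81% power at the final look and 82% over both. That stands, and it makes the proportion reading the more likely source of the numbers. It does not settle the plan: SAP 2 and 4.1 still print the annual rate beside the sizes, and SAP 9 puts 15% in place of an 8% that Protocol 10.1 calls annual. Nor does a continuity correction appear in either document or in the logistic test of SAP 7.2.

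Three stronger readings are tempting, and the documents do not support them.

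- *A reader might infer that the final size was obtained by doubling the interim size.* Every final figure is exactly twice its interim figure, but SAP 4 says each was calculated, and ordinary formulas at 15% and 1:2 give nearly that ratio: 168.3/81.5 = 2.07 pooled, 184.6/93.5 = 1.97 corrected. The protocol's pair, 176 and 417 (ratio 2.37), rests on 1:4 allocation and another rate, so it is no benchmark.
- *A reader might infer that no calculation gives 80% for 188/376.* The corrected formula at 15% comes within 1 to 2 points.
- *A reader might infer that enrolment is set 30 to 80 residents too high.* That holds only for uncorrected tests. On the formula that reproduces 94, the need is 185/0.7 = 264 against 268. SAP 4 also states its sizes as upper estimates and calls the 94 unadjusted, so a small margin is not an error.

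**Conclusion.** The concern holds in this form: the 80% power stated for 188/376 does not follow from the inputs printed with it. On an annual 15% and 6 months' follow-up, two-look power for a 60% effect is about 39% to 64%, short of 80% by at least 16 points under every test tried. On 15% as a 180-day proportion, it is about 86% with the unadjusted Wald test and 82% to 92% across tests, so the label then understates the power and the sizes are adequate.

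The documents do not settle which basis applies. The near-match of the corrected formula favours the proportion, but that is an inference.

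The figures assume that every evaluable subject has a known outcome, that groups are independent, that the Pocock bounds apply at half information, and that propensity adjustment and matching neither add nor remove information. The adjusted analysis will differ somewhat, but these assumptions do not explain the gap between the two rate bases.

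**What to change.** 1. Reconcile SAP 4 with SAP 2 and 4.1: state whether 15% is a 180-day proportion or an annual rate, and give the window over which it was observed.
2. In SAP 2, 4 and 4.1, restate the power of 94/188 and 188/376 on that proportion under the SAP 7.2 test. For a 60% effect over both looks, expect about 86% if 15% is per 180 days, or about 40% to 64% depending on the test if it is per year.
3. For each look, print the control proportion over 180 days, the effect, the boundary, the test and any continuity correction.
4. Use the same control-proportion basis, boundary and test in the SAP 4.1.1 re-estimation, so that the event-rate update and matching rate are its only new inputs.

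The cost is one rerun of the group sequential calculation and wording changes. Restating the power needs no change in enrolment. If the annual reading is confirmed, the sponsor would also have to decide whether to accept the lower power or recalculate the final pair.
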